6.9. Secondary Endpoints and Analyses

Adverse device effects

The incidence and severity of adverse device effects (ADEs) will be summarized. ADEs/AEs will be considered treatment emergent if their onset occurs after initiation of the first insonification.

Any missing severity assessments will be assumed to be Grade 3, missing relationship assessments will be assumed to be related, and missing seriousness assessments will be assumed as serious in the relevant summaries.

An overview of treatment-emergent ADEs (TEADE) will be produced, including counts and percentages of subjects with any incidences of:

- TEADE
- TEADE related to study procedure
- Serious TEADE
- TEADEs leading to study discontinuation

ADE summaries will include the overall incidence (by system organ class and preferred term), events by maximum intensity, event by relationship to study procedure, events leading to discontinuation of study, and serious ADEs. ADEs will be graded according to National Cancer Institute Common Terminology Criteria for Adverse Events (NCI CTCAE v5.0).

Sponsor: GE Research
Protocol Number: GE-HUI-01
Version and Date: Final v2.0, 30JUN2021

Adverse events will be coded based on MedDRA. TEADEs will be summarized by system organ class (SOC) and preferred term (PT) in descending order of overall incidence. For these summaries, subjects will be counted once within a SOC/PT based on their TEAE having maximum severity or relationship, as applicable.

Summaries of adverse events by SOC and PT will include the following types:

- TEADEs;
- TEADEs related to study procedure
- CTCAE Grade 3 or higher TEADEs
- CTCAE Grade 3 or higher TEADEs related to study procedure
- Serious TEADEs
- TEADEs leading to study discontinuation
- UADEs

A summary of TEADEs by SOC, PT, and maximum severity will be prepared. Events with missing severity will be assumed to be Grade 3. A summary of TEADEs by SOC, PT, and maximum relationship will also be prepared. Events with missing relationship will be assumed to be Related.

A comprehensive listing of all ADEs will be provided in a by-subject data listing. In addition, the following listings will be provided:

- TEADEs related to study procedure
- Serious TEADEs
- TEADEs leading to study discontinuation

Clinically significant laboratory abnormalities

Laboratory abnormalities will be graded and evaluated for clinical significance.

The number and percent of subjects of subjects with a clinically significant laboratory abnormality will be summarized by laboratory parameter and study visit. In addition, a summary of laboratory toxicity grades will be prepared by laboratory parameter and study visit.

The denominator for percentages will be the number of subjects with data for the given parameter and visit.

Clinical chemistry and hematology parameters will be reported based on the International System of Units (SI). Observed values and changes from baseline for laboratory evaluations will be summarized at each visit post initiation of HUI. Baseline is defined as the last non-missing value collected prior to first hepatic ultrasound insonification.

A listing of laboratory abnormalities will be provided as will a listing of all laboratory parameters.

Vital signs

Sponsor: GE Research
Protocol Number: GE-HUI-01
Version and Date: Final v2.0, 30JUN2021

Absolute values and changes from baseline will be summarized for vital signs parameters at specified timepoints in the protocol Schedule of Events.

Vital signs include: systolic and diastolic blood pressure (mmHg), temperature (C), respiratory rate (bpm), and heart rate (bpm). Observed values and changes from baseline for vital signs will be summarized at each visit and time point.

All vital signs data will be listed.

Physical examination

A summary of physical examination (PE) findings will be presented by body system as recorded on the eCRF. The number of subjects and percent will be summarized based on abnormal examination results (abnormal without clinical significance and abnormal with clinical significance) by visit. The number and percent of subjects with any abnormal finding will also be provided. The denominator will be the number of subjects with a physical examination performed at the visit.

Physical examination findings will be listed by subject.

Electrocardiogram (ECG)

Absolute values and changes from baseline will be summarized for 12-lead ECG parameters at specified timepoints. The primary ECG endpoint will be QTcF.

ECG parameters include: QT interval (ms), PR interval (ms), QRS interval (ms), RR interval (ms), QTcF (ms). Observed values and changes from baseline for ECG data will be summarized at each visit and time point.

In addition to the continuous summary, the overall interpretation of ECG results will be summarized as within normal limits, abnormal without clinical significance, and abnormal with clinical significance by visit and time point.

All ECG data will be listed.

Whole-body insulin sensitivity

The effect of hepatic ultrasound insonification on changes from baseline in whole-body insulin sensitivity during a two-step HE Clamp will be assessed by:

- Insulin Sensitivity Index (SI)
- Glucose disposal rate during steady state (M)
- Glucose metabolic clearance rate during steady state (MCR)

The formulas for SI, M, and MCR are described in section 6.8. Each parameter will be summarized using descriptive statistics in the Ultrasound Insonification Effect Population.

Glucose tolerance and insulin secretion

To evaluate the effect of hepatic ultrasound insonification on change from baseline in glucose tolerance and insulin secretion, assessed by an oral glucose tolerance test (OGTT), area under the curve (AUC) total and incremental time (e.g., $AUC_{0-180\text{min}}$) will be calculated.

AUC is calculated according to the linear trapezoidal rule:

$$\frac{AUC(t_i)}{t_{i+1}} = \frac{C_i + C_{i+1}}{2} \times (t_{i+1} - t_i)$$

where C is glucose concentration (mg/dL) with measurements at times $t_1..t_n$ such that

$$AUC_{\text{total}} = \sum_{i=1}^{n-1} AUC(t_i)$$

$AUC_{0-180\text{min}}$ is similarly derived but uses data only through 180 minutes.

AUC results will be summarized using descriptive statistics in the Ultrasound Insonification Effect Population.

Glucose metabolism parameters

The effect of hepatic ultrasound insonification on glucose metabolism parameters will be evaluated by the following endpoints in the Ultrasound Insonification Effect Population:

- Blood glucose (BG) profiles assessed with continuous glucose monitoring system (CGMS)
 - Time spent in defined glucose ranges
 - Average daily glucose
 - BG variability parameters (e.g., coefficient of variation as percentage of mean level [% CV], etc.)
 - Low blood glucose index (LBGI)
 - High blood glucose index (HBGI)
- Homeostasis Model Assessment of Insulin Resistance (HOMA2-IR)
- Homeostatic Model Assessment of Insulin Secretion (HOMA2-B)
- Fasting plasma glucose (FPG)

The baseline period for CGMS parameters will be calculated using data starting from 14:00h on Day -1 to 22:00h on Day 1, omitting data collected between a subjects OGTT glucose consumption start time + 180 minutes.

The primary insonification analysis period for CGMS parameters will be from 14:00h on Day 15 to 22:00h on Day 16, omitting data collected between a subjects OGTT glucose consumption start time + 180 minutes.

The CGMS parameters will be summarized in a table using descriptive statistics for the primary insonification analysis period and change from baseline. The CGMS parameters for the baseline period, primary insonification analysis period and Days 19 and 20 will be listed.

The percent of time spent in defined glucose ranges will be calculated separately for each of the analysis periods along with the change from the baseline period. The following glucose ranges will be defined and presented separately:

- > 250 mg/dL (>13.9 mmol/L)
- > 180 mg/dL (>10.0 mmol/L)
- 70-180 mg/dL (3.9-10.0 mmol/L)
- < 70 mg/dL (<3.9 mmol/L)
- < 54 mg/dL (<3.0 mmol/L)

Average daily glucose will be calculated based on the applicable glucose measurements obtained during the specified day/period.

To calculate the LBGI and HBGI, the original BG data for each day/period is transformed such that it is centered by zero and bound between $-\sqrt{10}$ and $\sqrt{10}$.

$$f(BG, \alpha, \beta) = [(\ln(BG))^{1.084} - 5.381] * 1.509$$

The transformed values are then inputted into the BG risk function:

$$r(BG) = 10 * f(BG, \alpha, \beta)^2$$

The risk of each observation is further transformed into two series, risk of low BG series, $rl(BG)$, and risk of high BG series, $rh(BG)$:

$$rl(BG) = r(BG) \text{ if } f(BG) < 0 \text{ and } 0 \text{ otherwise}$$

$$rh(BG) = r(BG) \text{ if } f(BG) > 0 \text{ and } 0 \text{ otherwise}$$

These series are then averaged to produce the LBGI and the HBGI as follows:

$$LBGI = \frac{1}{n} \sum_{i=1}^n rl(x_i)$$

$$HBGI = \frac{1}{n} \sum_{i=1}^n rh(x_i)$$

Absolute values and changes from baseline will be summarized using descriptive statistics for BG, HOMA2-IR, HOMA2-B, and FPG. Baseline is defined as the last non-missing value collected prior to a subject's first HUI. The HOMA2 results will be produced by the HOMA2 calculator with fasting plasma glucose and insulin concentration obtained from safety laboratory

assessments as the inputs. Summaries will be provided by study visit/time point as applicable in the protocol Schedule of Events.

For BG, coefficient of variation (CV) calculated as $100 \times [\text{standard deviation (SD)} \div \text{mean}]$ will be included with the other summary statistics.

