10.1 Definitions

10.1.1 Adverse Device Effect (ADE)

An ADE is any undesirable and unintended medical event occurring to a subject in a clinical study, whether or not related to the study procedures. This includes events from the first study related activity after the subject has signed the informed consent and until post treatment follow-up period as defined in the protocol. The following should not be recorded as ADEs, if recorded as medical history/concomitant illness on the CRF at screening:

- Pre-planned procedure, unless the condition for which the procedure was planned has worsened from the first study related activity after the subject has signed the informed consent
- Pre-existing conditions found as a result of screening procedures
- Pre-existing events that has not worsened in intensity or frequency from baseline

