10.2 Procedures

10.2.1 Collection and Recording of ADEs

Collection of all ADEs (UADEs and ADEs) will commence from the time the subject signs the informed consent to participate in the study until the post-treatment follow-up

visit. At each study visit and throughout the in-house treatment period, the Principal Investigator will assess whether any subjective ADEs have occurred. In order to avoid bias in eliciting ADEs, a non-specific question, such as “How have you been feeling since your last visit?” may be asked. Subjects may report ADEs occurring at any other time during the study.

All subjects experiencing ADEs must be monitored and given appropriate medical treatment at the discretion and judgement of the Principal Investigator until the symptoms subside and any clinically relevant changes in laboratory values have returned to baseline or until there is a satisfactory explanation for the changes observed. All ADEs will be documented in the ADE page of the eCRF, whether or not the Principal Investigator concludes that the event is related to the treatment/procedure. The event term, start and stop dates, severity, action taken and outcome, will be documented.

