5.5. Imputation of Partial Dates

Adverse Device Effects (ADE) and Concomitant Medications

- If the start date is completely missing, no imputation will be conducted.
- If the start date is missing day and month, do the following:
 - If the start year does not fall in the same year as that of the HUI date or if the record contains information to indicate that the event ended before the HUI date (e.g. the event end date month and year are earlier than the HUI date or the full end date is known and occurs earlier than the HUI date), then set the start month and day to January 1st.
 - Otherwise, set the start date to the HUI date.
- If only the start day is missing, do the following:
 - If the start month and year does not fall in the same month and year as that of the HUI date or if the event contains information to indicate that the event ended before the HUI date, then set the start day to the 1st day of the month of the event start date.

- Otherwise, set the event start date to the HUI date.
- Event end dates will not be imputed.

These imputation rules will be applied similarly to ADE and concomitant medication dates.

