5.7. Missing Data

AE and concomitant medication date imputations are described in Section 5.5. Otherwise, missing data will not be imputed for any endpoint or analysis.

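### SAP 6.9 defines treatment emergence by onset alone, so an ADE that starts before Day 15 and worsens after insonification is left out of the TEADE tables and TEADE listings, and an ADE with no start date has no defined status

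*SAP*

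**What the plan says.** The treatment-emergent rule is one sentence in SAP 6.9: "ADEs/AEs will be considered treatment emergent if their onset occurs after initiation of the first insonification". The same section bases its main SOC/PT tables on TEADEs: all, related, Grade 3 or higher, Grade 3 or higher and related, serious, and leading to discontinuation. It also plans separate listings of related, serious and discontinuation TEADEs.

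For dates, SAP 5.5 says: "If the start date is completely missing, no imputation will be conducted". Partial start dates are treated differently. If month and day are missing, and neither the year nor the end information rules it out, the instruction is "Otherwise, set the start date to the HUI date". If only the day is missing, the matching instruction is "Otherwise, set the event start date to the HUI date". SAP 5.7 then closes the matter: "Otherwise, missing data will not be imputed for any endpoint or analysis".

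Other missing ADE fields get a worst-case value in SAP 6.9: "Any missing severity assessments will be assumed to be Grade 3, missing relationship assessments will be assumed to be related", and missing seriousness is taken as serious.

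Protocol 10.2.1 starts ADE collection at informed consent and lists the fields to be kept: "The event term, start and stop dates, severity, action taken and outcome, will be documented". Among the items that Protocol 10.1.1 keeps out of ADE recording, if they were noted at screening, is: "Pre-existing events that has not worsened in intensity or frequency from baseline".

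**The concern.** Before the first insonification on Day 15, subjects go through an OGTT, an overnight insulin infusion, a clamp with IV lines, and CGM sensor placements on Day -1 and Day 8. Protocol 10.3 names these procedures as sources of anticipated adverse effects. Non-serious ADEs are followed until recovering, recovered or the end of follow-up (Protocol 10.4), so an ADE may be open when insonification begins.

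The incidence and severity of ADEs, including liver injury, is the first-listed secondary objective. An existing event that becomes worse after exposure is one form that a device-related harm could take. A definition based on onset alone assigns that event to the pre-treatment period, which lowers the treatment-emergent count. A missing onset date with no assigned status can have the same effect, depending on how the programmer resolves it.

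**Working it through.** The documents give no figure to reproduce; the question is how the written rules classify particular events. The inputs are SAP 5.5 (date imputation), SAP 5.7 (no other imputation), SAP 6.9 (emergence) and SAP 5.2 (the HUI date is the date of the first insonification).

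**Step 1. Apply the rules to test cases.** The HUI date is set arbitrarily to 20 January 2021.

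| Case | Onset used | TEADE under SAP 6.9? |
|---|---|---|
| Full date, 21 January 2021 | 21 January | Yes |
| Full date, 8 January 2021, worsens after insonification | 8 January | No |
| Start date wholly missing | none | Condition cannot be evaluated; no status given |
| Day missing, January 2021 | 20 January | Yes, if the HUI date itself counts as after initiation |
| Month and day missing, 2021 | 20 January | Yes, on the same condition |
| Day missing, December 2020 | 1 December | No |
| Day missing, February 2021 | 1 February | Yes |

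The partial-date cases assume no evidence that the event ended before the HUI date. Two cases need attention: the worsening event, which fails the definition, and the undated event, which the definition does not settle. There is also a small ambiguity, because an imputed onset on the HUI date carries no clock time to compare with initiation.

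**Step 2. Look for another route into the TEADE outputs.** Protocol 10.2.1 requires start date, stop date and severity, but no new record when severity changes. Under Protocol 10.1.1 a condition noted at screening loses its exemption once it worsens, so it can be entered as an ADE. An ADE that first arises after consent has no equivalent provision.

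**Step 3. Find where the worsening event can still be seen.**
- SAP 6.9 plans a listing of all ADEs.
- Its general ADE summaries (incidence, maximum intensity, relationship, discontinuation, serious) and its UADE table are not expressly limited to TEADEs.
- Laboratory toxicity grades and clinically significant abnormalities are tabulated by visit, with changes from the last value before the first insonification. Protocol 12.1.4.3 adds shifts to the worst on-study value.
- Skin or IV-site reactions have no laboratory counterpart. Examination findings are tabulated by visit, but not by CTCAE grade, and skin is not among the systems that the abbreviated examination must cover (Protocol 9.1.4).

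**Step 4. Scale.** With n = 15, one subject is 1/15 = 6.7 percentage points. Exact (Clopper-Pearson) 95% intervals:
- 0/15 = 0%, interval 0 to 21.8% (upper limit 1 − 0.025^(1/15) = 0.218)
- 1/15 = 6.7%, interval 0.2 to 31.9%
- 2/15 = 13.3%, interval 1.7 to 40.5%

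**Step 5. Pre-treatment collection window.** Standard screening gives up to about 28 + 15 = 43 days before Day 15 (Day -1 plus Days 1 to 14 is 15 days). For extended screening, Table 16-2 starts at Day -50, giving about 50 + 14 = 64 days. Adding the 30-day minimum extension to 28 days would give 28 + 30 + 15 = 73. Days 15 to 28 are 14 days. These lengths show only the opportunity for earlier onsets, not how many events are open on Day 15 and later worsen.

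**The case against.** The strongest reply is that little is hidden. A reader might infer that a worsening event would be visible only in the all-ADE listing. The SAP does not support that: its general ADE summaries and UADE table carry no TEADE restriction, and Protocol 12.1.4.1 carries none either. Nor is a liver-enzyme rise a good example of a lost signal. It would show in the by-visit laboratory tables whatever its TEADE status. Under Protocol 10.1.2 a laboratory ADE must also require active management, so a Grade 1 rise may not be an ADE until it becomes clinically significant, and its onset could then fall after insonification. These points stand. They do not restore the event to the TEADE tables. A single record with a pre-treatment start date also need not show when the grade rose, and the general summaries do not separate time before insonification from time after it.

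A reader might also infer that ADEs open on Day 15 are to be expected. No event rate is given, the Period 1 OGTT and clamp are about two weeks earlier, and the first CGM sensor is changed on Day 8. Such events are possible; their frequency is unknown.

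On undated events, a reader might infer that the SAP excludes them outright. It does not: it withholds imputation and says nothing about status. Start dates are a required field and queries are resolved before sign-off, so these cases should be rare.

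Finally, the eCRF Completion Guidelines and Data Management Plan are not available here and might already call for a new line on worsening. If so, the first gap closes in practice, though the SAP would still need to say so.

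**Conclusion.** The point holds as a gap in the definition. As written, an ADE with onset between consent and the first insonification that later rises in grade, becomes serious or causes discontinuation is not a TEADE, and is absent from the TEADE tables and the three TEADE listings. An ADE with no start date has no assigned status. It is the one ADE field covered by neither the worst-case rules nor the conservative partial-date rule.

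The loss is from the treatment-emergent outputs, not from all reporting. Its size depends on how many such events occur, which the documents do not allow anyone to estimate; each affected subject is 6.7 percentage points at n = 15. The conclusion assumes that no document outside the protocol and SAP requires a new record on worsening. It concerns the safety objective only and leaves the clamp endpoints untouched. It should be corrected because the error runs in the favourable direction and the remedy is small.

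**What to change.** In SAP 6.9, define a TEADE as an ADE that starts, or increases in CTCAE grade or becomes serious, on or after initiation of the first insonification. Add that an ADE with a wholly missing start date counts as a TEADE unless its end date precedes the first insonification, and that onsets imputed to the HUI date qualify.

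In the eCRF instructions, require a grade increase after the first insonification to be recorded with its own date. If data entry is closed, review every ADE ongoing at the first insonification for later worsening, and describe the change in the CSR, as SAP 7 provides for changes to the planned analyses.

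The cost is a few sentences in the SAP and one data-entry instruction, or a short record review in a study of about 15 subjects. TEADE counts may be slightly higher, which matches the direction the SAP already takes for missing severity, relationship and seriousness.

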5.2 Secondary Objectives and Endpoints

To evaluate safety and tolerability of hepatic ultrasound insonification in subjects with T2DM, assessed by:

- Incidence and severity of adverse device effects (ADEs) [including, liver injury]
- Incidence and severity of clinically significant laboratory abnormalities
- Change from baseline in vital signs (blood pressure, temperature, respiratory rate, and heart rate)
- Incidence and severity of clinical findings on physical examination
- Change from baseline in 12-lead electrocardiogram (ECG) parameters; the primary ECG endpoint will be QTcF

To evaluate the effect of hepatic ultrasound insonification on changes from baseline in whole-body insulin sensitivity during a two-step hyperinsulinemic, euglycemic clamp (H-E Clamp), assessed by:

- Insulin Sensitivity Index (SI)
- Glucose disposal rate during steady state (M)
- Glucose metabolic clearance rate during steady state (MCR)

To evaluate the effect of hepatic ultrasound insonification on change from baseline in glucose tolerance and insulin secretion, assessed by an oral glucose tolerance test (OGTT)

- Area under the curve (AUC), total and incremental time, e.g., $AUC_{0-180\text{min}}$

To evaluate the effect of hepatic ultrasound insonification on glucose metabolism parameters, assessed by:

- Change from baseline in blood glucose (BG) profiles assessed with continuous glucose monitoring system (CGMS)
 - Time spent in defined glucose ranges

- Average daily glucose
 - BG variability parameters (e.g., coefficient of variation as percentage of mean level [% CV], etc.)
 - Low blood glucose index (LBGI)
 - High blood glucose index (HBGI)
- Change from baseline in Homeostasis Model Assessment of Insulin Resistance (HOMA-IR)
 - Change from baseline in Homeostatic Model Assessment of Insulin Secretion (HOMA-B)
 - Change from baseline in fasting plasma glucose (FPG)

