12.1.4.3 Clinical Laboratory Assessments

Absolute values and changes from baseline will be assessed for hematology, serum chemistry and urinalysis parameters. Post-baseline shifts in parameter values will be presented for the worst on-study observed values. Clinically significant laboratory parameters will be listed.

All laboratory data will be listed and will include a flag for abnormal high or low values and clinically significant results.

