5.6. Multiple Assessments and Visit Windows

Nominal visits (e.g. those identified by the study CRF) will be the basis of summarization and statistical analysis; no visit date windowing will be conducted. Unscheduled data may be included in summaries of most extreme and baseline, summaries of specific abnormalities any time post-baseline, and subject data listings.

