7. CHANGES TO THE PLANNED ANALYSIS

Analyses and data presentations described in the protocol have been expanded upon, but no other changes were made to analyses specified in the protocol. Any changes to the planned analyses as detailed in this SAP will be described in the CSR.

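### SAP 6.9 omits the protocol's shift to the worst on-study laboratory value and tabulates laboratory abnormalities only by nominal visit, while SAP 7 says that no protocol analysis was changed

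*SAP*

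**What the plan says.** The endpoint, in protocol 5.2 and again in SAP 2.2, is "Incidence and severity of clinically significant laboratory abnormalities". It is not tied to any one visit.

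Protocol 12.1.4.3 commits to a specific display for it: "Post-baseline shifts in parameter values will be presented for the worst on-study observed values".

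SAP 6.9 plans the laboratory analysis differently. The number and percent of subjects with a clinically significant abnormality "will be summarized by laboratory parameter and study visit". For severity, "a summary of laboratory toxicity grades will be prepared by laboratory parameter and study visit". Observed values and changes from baseline are also given visit by visit. On percentages it says: "The denominator for percentages will be the number of subjects with data for the given parameter and visit". Abnormalities, and all laboratory values, are listed.

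SAP 5.6 sets the general rule: "Nominal visits (e.g. those identified by the study CRF) will be the basis of summarization and statistical analysis". It then allows, but does not require, unscheduled data in summaries of extreme values and of abnormalities at any time after baseline. SAP 6.9 defines no laboratory summary of either kind.

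SAP 7 states that protocol analyses were expanded upon but that "no other changes were made to analyses specified in the protocol".

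**The concern.** Incidence and severity are per-subject quantities: how many subjects were ever affected after the first insonification, and how badly. A set of visit-specific counts does not answer either question, because it does not show whether the subjects counted at one visit are those counted at the next. The protocol's worst-value shift would answer both, and would also show which subjects were already abnormal before treatment.

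At stake is a named secondary safety endpoint in a first look at repeated hepatic insonification in this population, where liver enzymes and bilirubin are the obvious parameters to examine. The omission is also undeclared. Protocol 12.1 says that the SAP will report changes to the protocol's analyses, and SAP 7 reports none.

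**Working it through.** The documents give no calculated figure on this point. The sample size of 15 was set empirically, and no expected abnormality rate is stated. The check is mainly a comparison of texts; the counts below are assumed, to show scale.

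**1. Side by side**

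| Feature | Protocol 12.1.4.3 | SAP 6.9 |
|---|---|---|
| Shift from baseline to worst value | Required | Not specified |
| Maximum grade per subject | Follows from the worst-value shift, if graded | Not specified; grades by visit |
| Subjects affected at any time | Obtainable from the shift | Not specified; counts by visit |
| New versus already present | Visible in the shift | Not separated in the count tables |
| Unscheduled values | Covered by worst on-study | No table that would use them |
| Listings | Yes, with flags | Yes |

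**2. When values can arise.** In protocol Table 16-2, hematology, chemistry and urinalysis fall at Screening and on Days -1, 15, 18 and 28. Protocol 6.2 places the Day 15 sample before the first insonification, so the scheduled post-treatment panels are Days 18 and 28, which are 28 − 18 = 10 days apart. The synopsis mentions safety bloods on Day 22, but section 6.2 names only fasting glucose among that day's blood tests and the table shows no chemistry. Protocol 9.1.8 foresees retesting of abnormal results, so off-schedule values are to be expected.

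**3. What by-visit counts can say about incidence.** With *a* subjects abnormal at Day 18 and *b* at Day 28 among *N* with data at both, the number ever abnormal at a scheduled visit lies between max(*a*, *b*) and min(*N*, *a* + *b*). Assume *a* = *b* = 2 and *N* = 15:

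- lower bound: 2/15 = 13.3%
- upper bound: 4/15 = 26.7%

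The planned laboratory tables cannot narrow this range. If some subjects lack one panel, the per-visit denominators also differ, and the two percentages no longer share a base.

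**4. Unscheduled values.** Assume three different subjects out of 15: one abnormal only at Day 18, one only at Day 28, one only at an unscheduled draw. Exact (Clopper-Pearson) 95% intervals are shown for the per-subject summaries.

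| Summary | Result |
|---|---|
| SAP 6.9, Day 18 | 1/15 = 6.7% |
| SAP 6.9, Day 28 | 1/15 = 6.7% |
| Any time, scheduled visits only | 2/15 = 13.3% (1.7% to 40.5%) |
| Any time, unscheduled values included | 3/15 = 20.0% (4.3% to 48.1%) |

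**5. New versus pre-existing.** Protocol 7.2, criterion 14, gives ALT or AST above twice the upper limit of normal as its example of an excluding result, so milder elevations at entry are possible. A subject abnormal on the pre-insonification Day 15 sample and unchanged at Day 18 is counted at Day 18 in the same way as a new case. The mean change from baseline does not classify individual subjects.

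**6. What reaches another table.** Protocol 9.1.8 requires every clinically significant laboratory abnormality to be recorded as an adverse device effect (ADE). SAP 6.9 tabulates treatment-emergent ADEs by system organ class and preferred term, counts each subject once at maximum severity, and adds a Grade 3 or higher table. Those tables do not depend on nominal visits. Protocol 10.1.2, however, defines a laboratory ADE more narrowly, as one severe enough to need active management. Graded elevations not judged clinically significant have no route into the ADE tables at all.

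**The case against.** The strongest reply is that the ADE tables already do the job. A clinically significant enzyme peak, scheduled or not, should be recorded as an ADE and counted once per subject at its worst grade. Those tables admit only events starting after the first insonification, and liver injury is itself named under the ADE endpoint. This largely stands. A reader might infer that the plan produces no any-time incidence whatever; the documents do not support that. The reply does not cover elevations that are graded but not recorded as ADEs, the tension between protocol 9.1.8 and 10.1.2, or the shift display that the protocol promised.

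A reader might also infer that a retest prompted by a clinically significant Day 18 result lowers the reported incidence. It does not: that subject is already counted at Day 18, and only the tabulated grade could be too low. Incidence in the laboratory tables is affected only when a subject's sole qualifying value is unscheduled.

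Third, SAP 5.6 permits unscheduled data in extreme-value and any-time summaries, and SAP 7 withdraws nothing, so the shift may still be intended. This is fair as to intent: the SAP does not order such data to be excluded. But permission to use data in a table that is not specified yields no table.

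Finally, with about 15 subjects, one arm and complete listings, a reader can count by hand. No data are lost. The protocol nevertheless promised the shift in addition to listings. Nor can a worst-value table recover values that were never drawn, so the 10-day interval is a matter of sampling and not of analysis.

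**Conclusion.** The point holds in a limited form. SAP 6.9 leaves out a laboratory display that the protocol requires, and the no-change statement in SAP 7 is inaccurate as the SAP stands. The laboratory tables as specified cannot give per-subject any-time incidence or maximum grade, cannot separate new from pre-existing abnormalities, and have no stated place for a value seen only off schedule.

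The size cannot be estimated from the documents, which give no expected rates. In the illustrations, two abnormal subjects at each post-treatment panel leave incidence anywhere from 13.3% to 26.7%, and three subjects affected (20.0%) appear as 6.7% at each of two visits. Both assume 15 subjects with complete panels; the second also assumes that each subject is abnormal on one occasion only. Where the abnormality is judged clinically significant and recorded as an ADE, the once-per-subject ADE tables should capture it. The remaining gap is therefore graded elevations not recorded as ADEs, and the laboratory endpoint's own tables. It should be corrected, but it does not touch the primary endpoints.

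**What to change.** - **SAP 6.9:** add a table of baseline grade by worst grade after the first insonification, per subject and parameter, including ALT, AST, alkaline phosphatase and total bilirubin.
- **SAP 6.9:** add an any-time row giving the number and percent of subjects with a new or worsened clinically significant abnormality after the first insonification.
- **Denominator:** use subjects with at least one value for the parameter after the first insonification, shown beside the Safety population N. Protocol 6.2 and 9.1.24 allow subjects to be excluded on Day 15 during the first insonification; dividing by the whole Safety population would count any who have no later panel as normal.
- **SAP 5.6:** state that unscheduled values *will*, not *may*, enter these two summaries.
- **SAP 7:** correct the no-change statement. If the sponsor prefers not to produce the shift, declare and justify the omission there.

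The cost is one or two tables from data already collected, plus SAP wording. No additional sampling is needed.
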